2. OBJECTIVES

2.1. Primary objectives

The primary objectives of this clinical trial are:

- To evaluate the safety and tolerability of recMAGE-A3 + AS15 ASCI compared to recMAGE-A3 + AS15 ASCI in combination with Poly IC:LC in patients with resected stage IV melanoma.
- To evaluate the immunogenicity of recMAGE-A3 + AS15 ASCI compared to recMAGE-A3 + AS15 ASCI in combination with Poly IC:LC as measured by antibodies serum titers (such as anti-MAGE-A3) in patients with resected stage IV melanoma.

Refer to Section 10.1 for the definition of the primary endpoints.

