3. STUDY DESIGN OVERVIEW

3.1. Study design

This is an open, randomized, two-arm, Phase II study in MAGE-A3 positive patients with completely resected stage IV melanoma to assess the safety, tolerability, immunogenicity and clinical activity (RFS and OS) of recMAGE-A3 + AS15 ASCI in combination with Poly IC:LC as adjuvant therapy compared to recMAGE-A3 + AS15 ASCI alone.

Patients will be randomized (1:1 ratio) to receive either recMAGE-A3 + AS15 ASCI or recMAGE-A3 + AS15 ASCI in combination with Poly IC:LC.

[figure not shown]

Figure 1. Overview of Study Design.

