10.1.1. Safety and tolerability endpoints

Occurrence of adverse events up to 30 days after each study dose, including abnormal haematological and biochemical parameters.

Occurrence of serious adverse events and autoimmunity during the whole study duration (up to 30 days after the last administration of study treatment). For methods of analysis, see Section 10.7.5.

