The sample size for this trial is calculated based on the primary immune endpoint of a serologic response to treatment. In a GSK trial using recMAGE-A3 + AS15 ASCI in a similar patient population, the total anti-MAGE-A3 IgG antibody measured at approximately 6 months at the first vaccine of the maintenance phase for the ASCI arm without Poly IC:LC had a geometric mean of about 7,000 and a standard deviation of no more than 0.28 on the log scale. It is anticipated that the ASCI arm with Poly IC:LC will further increase such anti-MAGE-A3 IgG antibody measurement at 6 months to about 10,500 for a 50% enhancement of the effect. Therefore, 20 patients per arm will yield 62% power for such detection of the anti-MAGE-A3 IgG antibody difference between the two arms at a one-sided significance level of 0.05. Power calculations for this trial will be only for the immune primary endpoint, since little toxicity is expected from either of the treatment arms on which to base a power calculation. Table 1 lists the change in power if the standard deviation deviates from the assumed value of 0.28 when everything else is the same. We plan to enroll 20 patients per arm for a total of 40 patients. To account for an approximate 10% loss-to-follow-up rate in this study, up to 44 patients may be enrolled.

The change in power if the standard deviation deviates from the assumed value of 0.28:

Standard Deviation	0.28	0.26	0.24	0.22	0.20
Power	0.62	0.68	0.74	0.80	0.86

A median RFS of about 8 months was observed for similar patients treated without adjuvant therapy. A median RFS of 12 months is expected of patients treated with recMAGE-A3 + AS15 ASCI alone in resected stage IV melanoma. Adding Poly IC:LC to this ASCI regimen might double the median RFS to 24 months. The power calculation shows that 20 patients per arm would have a power of about 61% for detecting such difference in RFS between the two arms with a one-sided type error rate of 0.05, assuming an accrual rate of 2.5 patients per month and a 3-year follow-up after the completion of accrual.

Assuming an accrual rate of 2.5 patients per month, it would take up to 18 months to enroll 44 patients to this trial.

Data Analyses Plan

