The descriptions and grading scales found in the CTEP Active Version of the NCI Common Terminology Criteria for Adverse Events (CTCAE v.4) will be utilized for AE reporting. The CTEP Active Version of the CTCAE is identified and located on the CTEP website at: http://ctep.cancer.gov/protocolDevelopment/electronic_applications/ctc.htm. All appropriate treatment areas should have access to a copy of the CTEP Active Version of CTCAE. Toxicity data will be summarized using the usual toxicity table by category and worst grade for the two ASCI regimens.

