10.7.5. Analysis of safety

The safety analyses will be based on the Total Treated population.

The duration of treatment and total number of doses of investigational product administered will be summarized by treatment group.

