10.7.5.1. Adverse events

Adverse events (AEs), including abnormal laboratory values, will be graded according to the CTCAE, Version 4.0 and coded to the preferred term (PT) level using the MedDRA dictionary.

The percentage of patients with adverse event(s) within 30 days of each recMAGE-A3 + AS15 ASCI dose +/- Poly IC:LC will be reported by treatment group with exact 95% confidence intervals, as per MedDRA terminology, by Preferred Term (PT) and System Organ Class (SOC), if appropriate. The same tabulation will be presented for grade 3, grade 4, related, grade 3 related and grade 4 related events, if appropriate.

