10.7.5.2. Serious adverse events

Serious adverse events occurring at any time after study initiation will be summarized by treatment group and described in detail by patient narratives.

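### The first primary objective compares the arms on safety, but no between-arm estimate is planned for adverse events or serious adverse events

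*Combined protocol and SAP*

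**What the plan says.** Section 2.1 gives the first primary objective as: "To evaluate the safety and tolerability of recMAGE-A3 + AS15 ASCI compared to recMAGE-A3 + AS15 ASCI in combination with Poly IC:LC". The matching endpoint in 10.1.1 starts with "Occurrence of adverse events up to 30 days after each study dose" and continues with SAEs and autoimmunity.

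The analyses that serve this objective are:

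- **Adverse events (10.7.5.1):** the percentage of patients with an event, "reported by treatment group with exact 95% confidence intervals", by preferred term and system organ class, repeated by grade and relatedness.
- **Toxicity table (10.3, Data Analyses Plan):** "Toxicity data will be summarized using the usual toxicity table by category and worst grade for the two ASCI regimens".
- **SAEs (10.7.5.2):** "summarized by treatment group and described in detail by patient narratives".
- **Population (10.7.5):** "The safety analyses will be based on the Total Treated population".

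On numbers, 10.3 states: "We plan to enroll 20 patients per arm for a total of 40 patients". Up to 44 may be enrolled to allow for losses. The same section says that power was worked out for the immune endpoint alone, because little toxicity was anticipated.

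**The concern.** The objective is comparative, but each adverse event and SAE analysis stops at description within an arm. The plan does specify between-arm methods elsewhere. Antibody titre gets a two-sample t test on the log scale (10.3). Relapse-free survival gets a Cox model and a log-rank test (10.3, 10.7.3.1.1). Within the safety section only time to death has a between-arm model, by reference to 10.7.3, and that does not measure toxicity. The general 0.05 significance threshold in 10.4.3 is not attached to any safety contrast.

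Two things are at stake. First, the primary safety question would be reported without a planned estimate of how much toxicity Poly IC:LC adds, or of how uncertain that amount is. Second, the estimate may be improvised later. The trial is open-label, and 10.7.5.1 spans every preferred term, organ class, grade and relatedness category. Choosing categories and a method after the data are seen leaves room for selective emphasis.

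**Working it through.** **Inputs.** n = 20 per arm (10.3), 1:1 allocation (3.1), 95% exact intervals per arm (10.7.5.1). The Total Treated population could reach 44/2 = 22 per arm; 20 is used here. The documents give no toxicity rates for this trial, so all rates below are assumptions.

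**The plan's own figure.** There is none for toxicity. The only primary-endpoint power is 62%, for antibody titre. It reproduces: a t test with 38 degrees of freedom, difference log10(10,500/7,000) = 0.176, SD 0.28 and one-sided 0.05 gives 0.621. It says nothing about safety.

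**Step 1: formulas.** With x events out of n and p = x/n:

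- Exact (Clopper-Pearson) limits: lower = Beta quantile(0.025; x, n − x + 1); upper = Beta quantile(0.975; x + 1, n − x).
- Wilson limits l, u = [p + z²/(2n) ± z·√(p(1 − p)/n + z²/(4n²))] / (1 + z²/n), with z = 1.96.
- Newcombe interval for d = p2 − p1: from d − √[(p2 − l2)² + (u1 − p1)²] to d + √[(u2 − p2)² + (p1 − l1)²].

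**Step 2: one example, 2/20 against 10/20.**

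- Exact intervals: 1.2 to 31.7% and 27.2 to 72.8%. They overlap, since 27.2 < 31.7.
- Wilson limits: 2.8 to 30.1% and 29.9 to 70.1%.
- Newcombe lower limit: 0.40 − √[(0.50 − 0.299)² + (0.301 − 0.10)²] = 0.40 − 0.284 = 0.116.
- Newcombe upper limit: 0.40 + √[(0.701 − 0.50)² + (0.10 − 0.028)²] = 0.40 + 0.213 = 0.613.
- So the difference is 40 points, 95% interval 12 to 61; two-sided Fisher p = 0.014.

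Against 2/20, the exact intervals do not separate until the other arm has 12/20. The Newcombe interval excludes zero from 8/20 (2.9 to 52.5 points), and Fisher reaches 0.05 at 9/20.

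**Step 3: all possible outcomes.** Sum the product of the two Binomial(20, p) probabilities over the 21 × 21 outcome pairs that meet each criterion:

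| Assumed true rates | Exact intervals separate | Newcombe interval excludes 0 | Fisher p ≤ 0.05 (two-sided) |
|---|---|---|---|
| 5% v 15% | 0.2% | 9% | 7% |
| 10% v 20% | 0.5% | 11% | 7% |
| 10% v 30% | 4% | 34% | 24% |
| 10% v 40% | 16% | 62% | 49% |
| 10% v 50% | 37% | 84% | 74% |
| 10% v 60% | 63% | 95% | 91% |
| 20% v 50% | 12% | 53% | 41% |
| 20% v 60% | 31% | 75% | 65% |

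With equal true rates between 10% and 50%, the exact intervals separate in 0.01 to 0.2% of trials. The Newcombe interval excludes zero in 1.7 to 5.3%. Separation is therefore a much stricter criterion than a 95% comparison.

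**The case against.** The strongest reply is that descriptive, by-arm safety reporting is a reasonable choice in a 40-patient phase II trial. The plan says openly that safety is unpowered, sets no safety hypothesis or margin, and makes by-arm presentation its main analysis (10.4.2). Because it reports percentages in arms of about 20, any reader can work out the difference and its interval, so no information is lost. That stands, and it limits the point to a missing planned estimate. It does not explain the omission: an interval for a difference needs no power claim, and expecting little toxicity justifies only the absence of a power calculation.

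A reader might infer that the plan intends to judge the arms by interval overlap, or that it leaves the safety question unanswerable. Neither is supported. No section states an overlap rule, and by-arm rates, the worst-grade table and the SAE narratives do form a descriptive comparison. Nor would overlap hide every real difference: at 10% against 60% the intervals separate in 63% of trials.

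It is also fair to say that sample size is the larger limit for uncommon events. At 10% against 20%, the difference interval excludes zero in only 11% of trials, and the categories of most interest may well be rare. The proposed change does not cure that.

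**Conclusion.** The gap is real and modest in size. A comparative primary objective has no specified between-arm estimate or interval for adverse events or SAEs, and this follows from the text without any assumption. How poorly the per-arm intervals would serve as a substitute does depend on assumed rates at 20 per arm. For a control rate of 10% and differences of 20 to 40 points, they separate in 4 to 37% of trials, against 34 to 84% for a difference interval. For differences of 10 points both are low.

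The difference interval would not make the trial powered for toxicity, and an interval that includes zero would not show equal safety. For example, with no events in either arm the Newcombe interval is ±z²/(n + z²) = ±3.84/23.84, or about ±16 points. Reporting that range is the main benefit, since it shows how much added toxicity the data cannot exclude.

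**What to change.** In 10.7.5.1 and 10.7.5.2, add the risk difference (Poly IC:LC arm minus control) with a Newcombe or exact 95% interval. Restrict it to a short list fixed in advance:

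- any related Grade 3-4 adverse event
- any SAE
- any potential immune-mediated disease
- stopping study treatment because of an adverse event

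Name the interval method and the counting window for each item. State that the intervals are estimates, not tests, and that including zero is not evidence of equal safety. Keep the per-arm exact intervals, the worst-grade table and the narratives.

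The cost is one column in tables already planned, using the software listed in 10.7 and data already collected. The small downside is a few more intervals without multiplicity adjustment (10.4.3 plans none), which is why the list should stay short.

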10.7.5.2. Serious adverse events

Serious adverse events occurring at any time after study initiation will be summarized by treatment group and described in detail by patient narratives.

10.7.5.3. Deaths

Time to death will be analyzed as described in Section 10.7.3. Causes of death (e.g., hematological toxicity, non-hematological toxicity, disease under study, or other) will be summarized by treatment group.

10.7.5.4. Concomitant medications

For the analysis of the use of concomitant medications, the Total Treated population will be considered. Patients, for whom no use of concomitant medications has been reported, will be considered as patients without any use of concomitant medications.

10.8. Gene profile analyses and translational research

10.8.1. Gene profile

The gene profile will be evaluated by an interaction test between the treatment status (recMAGEA3+AS15 versus recMAGEA3+AS15 in combination with Poly IC:LC) and the gene signature status (positive versus negative) in a Cox regression analysis using the secondary clinical endpoint (RFS) as dependent variable in an exploratory hypothesis driven analysis.

11. CONDUCT OF THE STUDY

11.1. Ethics and regulatory considerations

The study will be conducted according to Good Clinical Practice (GCP), the Declaration of Helsinki (US 21 CFR Part 50—Protection of Human Patients, and Part 56— Institutional Review Boards) and local rules and regulations of the country.

CONFIDENTIAL

Submission of the protocol and any protocol amendments to regulatory agencies will occur in accordance with local regulatory requirements at the Moffitt Cancer Center.

11.1.1. Institutional Review Board/Independent (IRB/IEC)

The IRB/IEC must be constituted according to the local laws/customs of each participating country. The ICH Harmonized Tripartite Guideline for Good Clinical Practice recommends that the IRB/IEC should include:

- a. At least five members.
- b. At least one member whose primary area of interest is in a non-scientific area.
- c. At least one member who is independent of the institution/ study site.

Only those IRB/IEC members who are independent of the investigator and the sponsor of the study should vote or provide opinion on a study-related matter.

A list of IRB/IEC members, their professions and other qualifications should be obtained by the Study Monitor.

This protocol and any other documents that the IRB/IEC may need to fulfil its responsibilities, including patient recruitment procedures and information about payments and compensation available to patients, will be submitted to the IRB/IEC by the Study Monitor. Written and dated unconditional approval from the IRB/IEC of the protocol and amendment (if any and applicable), written informed consent form, consent form updates (if any), patient recruitment procedure(s) (e.g. advertisements), and any other written information to be provided to patients must be in the possession of the investigator and sponsor, MCC, before commencement of the study. This approval must refer to the study by study title and number with exact protocol version and date, and should identify the documents reviewed and state the date of review. Relevant GSK Biologicals and Oncovir's data such as the Investigator Brochures will be supplied by the Study Monitor to the appropriate IRB/IEC for review and approval of the protocol. Verification of the unconditional approval of the IRB/IEC will be transmitted by the Study Monitor prior to shipment of treatment supplies and CRFs to the site.

No deviations from, or changes to, the protocol should be initiated without prior written sponsor and IRB/IEC approval of an appropriate amendment, except when necessary to eliminate immediate hazards to the patients or where permitted by all applicable regulatory requirements or when the change(s) involves only logistic or administrative aspects of the study (e.g., change of monitor(s), telephone number(s)). Administrative changes and amendments not submitted for approval are submitted to the IRB/IEC for information only. However, written verification that such documents were submitted should be obtained.

The IRB/IEC must be informed by the Sponsor of:

- all subsequent protocol amendments, informed consent changes or revisions of other documents originally submitted for review,
- serious and/or unexpected adverse events occurring during the study, where required,

CONFIDENTIAL

- all subsequent protocol administrative changes (for information, except for US studies),
- new information that may affect adversely the safety of the patients or the conduct of the study,
- an annual update and/or request for re-approval, where required,
- when the study has been completed, where required.

If a trial is prematurely terminated or suspended for reasons including, but not limited to, safety or ethical issues or severe non-compliance, the sponsor will promptly inform the regulatory authorities of the termination or suspension and the reason(s) for the termination or suspension. If required by applicable regulations, the investigator must inform the IEC/IRB promptly and provide the reason for the suspension or termination.

11.1.2. Informed consent

In obtaining and documenting informed consent, the investigator should comply with the applicable regulatory requirement(s), and should adhere to GCP and to the ethical principles that have their origin in the Declaration of Helsinki. Prior to the beginning of the trial, the investigator should have the IRB/IEC's written approval of the written informed consent form and any other written information to be provided to the patients.

Informed consent will be obtained in accordance with 21 CFR 50.25.

Freely given informed consent should be obtained from every patient prior to clinical trial participation.

Information should be given in both oral and written form whenever possible and as deemed appropriate by the IRB/IEC.

An investigator or designate will describe the protocol to potential patients face to face. The Informed Consent Form may be read to the patients, but, in any event, the investigator or designate shall give the patients ample opportunity to inquire about details of the study and ask any questions before dating and signing the Informed Consent Form.

While informed consent information can be presented to groups at an initial information session, each patient must be given the opportunity to individually pose questions to the investigator or designate prior to the patient dating and signing the Informed Consent Form.

The Informed Consent Form must be in a language fully comprehensible to the prospective patients. Informed consent shall be documented by the use of a written consent form approved by the IRB/IEC and signed and dated by the patients and by the person who conducted the informed consent discussion. The signature confirms that the consent is based on information that has been understood. All illiterate individuals will have the study and the Informed Consent Form explained to them point by point by the interviewer in the presence of an impartial witness. The witness will personally sign and date the consent form. Orally witnessed consent will replace written consent only in countries where the local custom is contrary or if the patient's incapacity precludes this and provided that the local legal obligations are fulfilled.

CONFIDENTIAL

Each patient's signed informed consent form must be kept on file by the investigator for possible inspection by Regulatory Authorities. The patients should receive a copy of the signed and dated written informed consent form and any other written information provided to the patients and should receive copies of any signed and dated consent form updates. Any amendments to the written information will be provided to the patients.

Both the informed consent discussion and the written informed consent form and any other written information to be provided to the patients should include explanations of the following:

- a. That the trial involves research.
- b. The purpose of the trial.
- c. The trial treatments and the probability for random assignment to each treatment.
- d. The trial procedures to be followed, including all invasive procedures.
- e. The patient's responsibilities.
- f. Those aspects of the trial that are experimental.
- g. The reasonably foreseeable risks or inconvenience to the patients and, when applicable, to an embryo, fetus or nursing infant.
- h. The reasonable expected benefits. When there is no intended clinical benefit to patients, the patients should be made aware of this.
- i. The alternative procedures or courses of treatment that may be available to patients and their important potential benefits and risks.
- j. The compensation and/or treatment available to patients in the event of trial-related injury.
- k. The anticipated prorated payment, if any, to patients or patients' guardians for participating in the trial.
- l. The anticipated expenses, if any, to patients for participating in the trial.
- m. That the patients' participation in the trial is voluntary and patients may refuse to participate or withdraw from the trial, at any time, without penalty or loss of benefits to which patients are otherwise entitled.
- n. That the monitor(s), the auditor(s), the IRB/IEC, and the regulatory authority(ies) will be granted direct access to the patient's original medical records for verification of clinical trial procedures and/or data, without violating the confidentiality of patients, to the extent permitted by the applicable laws and regulations and that, by signing a written informed consent, the patient authorize such access.
- o. That records identifying patients will be kept confidential and, to the extent permitted by the applicable laws and/or regulations, will not be made publicly available. If the results of the trial are published, patients' identity will remain confidential.
- p. That the patients will be informed in a timely manner if information becomes available that may be relevant to the patients' willingness to continue participating in the trial.
- q. The person(s) to contact for further information regarding the trial and the rights of trial patients, and who to contact in the event of trial-related injury.
- r. The foreseeable circumstances and/or reasons under which a patient's participation in the trial may be terminated.
- s. The expected duration of a patient's participation in the trial.
- t. The approximate number of patients involved in the trial.

The Sponsor has the final responsibility for the final presentation of the Informed Consent Form, respecting the mandatory requirements of local regulations. The consent form generated by the sponsor, MCC, must be approved (along with the protocol, and any other necessary documentation) by the IRB/IEC.

